## **10.2 Sample Size:**

Aim 1: Aim 1. We selected a focus group size of 8-10 subjects. As per Krueger and Casey’s “Focus groups: A practical guide for applied research,” the ideal size of a focus group is 8-10 subjects because participants in a smaller focus group may feel pressure to talk more than they would otherwise, while larger focus groups will limit detail of participants’ responses who may feel pressure to share airtime.

Aim 2: A sample size of 18 patients was selected to achieve three goals. First, we estimated 162 RIC transplants per year over the past three years, with approximately 33% (54 patients) being performed inpatient, and estimated that approximately 33% could be enrolled, resulting in an achievable pilot sample size of 18 patients. Second, we ensured that the “rule of 10” for binary outcomes, wherein at least 10 participants per arm allows for reliable estimates in pilot studies (10 total in a single arm pilot, such as ours), was met. Third, we wanted to ensure that there were sufficient patients in three smaller cohorts to allow for an iterative process of improving the technology over the course of the pilot study, as per the guidance from the NIH SBIR process. With six patients per cohort, we should be able to achieve sufficient data for assessing usability.

## **10.3 Milestones and Success Criteria:**

**PRIMARY:** Retention rate in protocol from enrollment to hospital discharge or three weeks (whichever comes first) of over 66%.

**SECONDARY:** Patient satisfaction rate with avatar in the final cohort of 80%; rate of completion of 80% of the HCT educational modules of 75%; rate of completion of post- pilot survey within 1 week of discharge of 90%.

**10.4 Risk Mitigation and Alternative Strategies:** After each group of 5 we will assess patient feedback and modify the avatar program; this iterative design will allow for rapid protocol improvements to be deployed to new patients in subsequent cohorts to move towards achieving the success criteria above. In case outcomes are disappointing during the first cohort, we may switch to a more frequent iteration rate, in conjunction with the advice of our consulting biostatistician.

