## 6.0 Study Timelines

*Aim 1:* Prior to enrollment of the initial cohort of patients, we will convene a one-time 60minute focus group led by [name] PhD ([[name]\\[contact]](mailto:[contact])), a Senior Research Scientist in qualitative research, to discuss perspectives and opinions on implementing care.coach technology for HCT patients including education domains to include, frequency of avatar interactions, and anticipated staff concerns. This analysis will inform changes to be applied to the avatar, including script adjustments, prior to introducing the technology to patients in Aim 2.

*Aim 2:* We will complete the initial implementation of multiple HCT-related avatar changes across each of the categories in Section 2.2 and integrate them into an overall program schedule within 3 months. In the next 6 months, the HCT avatar program will then be piloted and iteratively improved through a phased, iterative user acceptance study with 3 consecutive cohorts of 6 RIC HCT patients each, receiving the avatar for up to 3 weeks per cohort (or patient discharge). After each cohort, user feedback will be gathered in the post-pilot survey (one week after disenrollment; see Appendix A), and protocol completion and patient-avatar engagement data will be analyzed.

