## 7.0 Study Endpoints

7.1 *Aim 1:* Modifications to an avatar-based human-staffed artificial intelligence technology platform for use in an inpatient HCT setting, derived from thematic analyses of a focus group of DF/BWH Cancer Center HCT nurse navigators, inpatient HCT nurses, and HCT physicians and extenders (as described in Section 8.4)

7.2 *Aim 2:* PRIMARY: Retention rate in protocol from enrollment to hospital discharge or three weeks (whichever comes first). SECONDARY: Patient satisfaction rate with avatar in the final cohort; rate of completion of 80% of the HCT educational modules; rate of completion of post-pilot survey.

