#### **8.5 Aim 2 Study Calendar**

**Table 1.** Study Calendar

Study Procedures	Baseline	Day 5 (<math>\pm 2</math>)	-1 to 0 days prior to discharge	One week after pilot (+ 5 days)
Informed Consent of participant	X			
Demographic data: self-report and EHR review	X			
Setting up avatar device	X			
RA check in		X	X	
Disenroll patients and retrieve avatar device from participants			X	

Post-pilot survey				X
-------------------	--	--	--	---

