## 9.0 Data and Specimen Banking

9.1 **Data Collected by care.coach:** Only meta-data will be collected through the avatar device. care.coach will be provided with a first-name, study-assigned patient number, and in-hospital location for safety functions, but will not be provided with other PHI. Upon completion of the study, name and in-hospital location data will be decoupled from other data and destroyed by care-coach. Audiovisual streams are recorded for immediate language processing and understanding but will not be stored post-processing. See Appendix C for care.coach security protocols.

9.2 **Data Collected by Dana-Farber:** No specimens will be collected or stored as part of this study. We will collect data on feasibility outcomes (retention, satisfaction, completion of modules) via post-pilot survey administered by the RA in person, at first follow up at Dana-Farber after discharge, or via telephone (Appendix A). Components of post-pilot survey questions on technology usability (Q1-19) were adapted from a published system usability scale. Questions on self-efficacy (Q20-28) were directly adapted from the General Self-Efficacy Scale. The remaining questions were newly developed for this study. Data will also be collected on patient demographics, transplant characteristics (type of transplant, donor characteristics, conditioning, GVHD prophylaxis, antibiotic prophylaxis, status of prior infectious diseases), and transplant outcomes (incidence and severity of GVHD, other infectious and non-infectious complications, relapse, survival). PHI will be stored with these data to allow for monitoring of long-term outcomes. Data will be stored on a secure server at DFCI up to 5 years from completion of the last study conducted as part of this project (dependent on whether we proceed to the Phase 2 study). One year after completion of the study, long-term analyses, and publication of deidentified findings, all PHI will be destroyed.

9.3 **Data Storage:** No specimens will be stored.

**9.4 Data Sharing:** Aggregated de-identified post-protocol survey data will be shared with care.coach; care.coach meta-data will not be shared with DFCI.

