Determine the rate of completion of the HCT educational modules.	75%
Determine the rate of completion of the post-pilot survey within one week of discharge.	90%

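### Table 1's late-only 5-day survey tolerance runs past the 1-week cut-off of the 90% survey criterion, so surveys done within the calendar can score as failures

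*Combined protocol and SAP*

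**What the plan says.** Two places give the scoring rule, and they agree. Section 10.3 states the secondary criterion as completion of the post-pilot survey: "pilot survey within 1 week of discharge of 90" percent. Table 2 in section 10.1 lists the same outcome as "Determine the rate of completion of the post-pilot survey within one week of discharge", with 90% beside it.

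Two other places give the scheduling rule. Table 1 in section 8.5 puts the survey in a column headed "One week after pilot (+ 5 days"). It puts disenrollment and device retrieval in a column headed, after a minus sign, "1 to 0 days prior to discharge". Section 6.0 says that "user feedback will be gathered in the post-pilot survey (one week after disenrollment; see Appendix A").

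Two further places bear on the timing without settling it. Section 7.2 lists the endpoint among "rate of completion of 80% of the HCT educational modules; rate of completion of post-pilot survey", with no window. Section 9.2 lets the research assistant give the survey "in person, at first follow up at Dana-Farber after discharge, or via telephone", with no day attached.

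**The concern.** The two rules use different starting points (discharge for scoring, end of pilot or disenrollment for scheduling) and different closing days. The calendar tolerance runs in one direction only. The check-in in the same table has a two-sided tolerance of 2 days, whereas the survey has plus 5 days and no early allowance. The permitted window therefore opens at about the point where the criterion closes.

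Staff who follow the calendar exactly could obtain a survey from every patient and still report a missed milestone. That result would reflect two unreconciled timing rules, not poor feasibility. With 18 patients the margin is narrow, so a couple of such surveys decide it.

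**Working it through.** **Inputs.** Sample size 18 (sections 4.0 and 10.2). Target 90%, closing 7 days after discharge (10.3, Table 2). Survey due 7 days after the pilot ends, tolerance +5 days (Table 1). Disenrollment on day -1 or day 0 relative to discharge (Table 1).

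**The plan's own figure.** Section 10.2 builds 18 from 162 transplants a year: 162 × 0.33 = 53.5 (stated as 54), and 54 × 0.33 = 17.8 (stated as 18). Using one third gives exactly 54 and 18. The sample size is reproduced.

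**Permitted window in days after discharge.** If disenrollment is on day d relative to discharge, the calendar permits the survey from day d + 7 to day d + 12, which is six days. The criterion counts it up to day 7.

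| Disenrollment | Permitted days after discharge | Days that count | Days that comply but fail |
|---|---|---|---|
| d = -1 | 6 to 11 | 6, 7 (two) | 8 to 11 (four) |
| d = 0 | 7 to 12 | 7 (one) | 8 to 12 (five) |

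The scheduled day (day 6 or day 7) passes in both rows. Only the tolerance conflicts. For a patient disenrolled on the day of discharge, day 7 is both the first permitted day and the last that counts.

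**Surveys needed.** 0.90 × 18 = 16.2, so 17 are needed.

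- 17/18 = 94.4%: met.
- 16/18 = 88.9%: missed.

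Two surveys done within the calendar but after day 7 are enough to miss the criterion when all 18 patients respond.

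**Sensitivity to the denominator.** The documents do not state the denominator for this rate, and 18 is assumed above. If only retained patients counted, the smallest number that meets the retention criterion of over 66% is 12 (12/18 = 66.7%; 11/18 = 61.1% does not meet it). Then 11/12 = 91.7% meets the survey target and 10/12 = 83.3% misses it. The number needed is 0.90 × n rounded up, which allows exactly one failure for every n from 10 to 18. The two-survey result does not depend on the choice within that range.

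**The case against.** The strongest reply is that a visit tolerance and a success criterion do different jobs. The tolerance says when a survey may be done without a calendar deviation, and the criterion says what counts. Section 10.3 and Table 2 give the same criterion, so a survey on day 9 is allowed and plainly does not count. Section 7.2 is shorthand that also leaves out the numerical targets, so its silence on the window is weak evidence. The scheduled day passes, and because the survey can be given by telephone, staff can time it.

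Most of this stands. The scoring rule is not ambiguous, and a team that surveys everyone on the scheduled day has no problem. What remains is that the calendar gives staff a window most of which the criterion rejects, and nothing in the text presents the criterion as a deliberately stricter timeliness measure.

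Three stronger readings are tempting, and the documents do not support them.

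- A reader might take 4 or 5 failing days out of 6 as a forecast that most surveys will be late. It is a count of days. The documents give no figure for how often the tolerance would be used.
- A reader might attach a probability of missing 90%. That would need an assumed on-time rate, and the result would measure how strict a 90% target is with 18 patients. It would be the same if the calendar already matched the criterion.
- A reader might infer from "receiving the avatar for up to 3 weeks per cohort (or patient discharge") in section 6.0 that some patients are disenrolled at three weeks while still in hospital, which would separate the two anchors further. Table 1 schedules disenrollment and device retrieval only on the day of discharge or the day before, section 8.4 has the device collected before discharge, and no length-of-stay data are given for these patients.

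**Conclusion.** The conflict is real and minor. Under Table 1 as written, the survey may be done up to day 11 or 12 after discharge, while the criterion in 10.3 and Table 2 stops at day 7. Two surveys inside the calendar but after day 7 give 88.9% against a target of 90%, even with full response.

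The conclusion rests on disenrollment on day -1 or 0, as Table 1 states, and on a denominator between 10 and 18. It says that the criterion can be missed in this way, not that it will be. The primary retention endpoint is unaffected, and section 10.3 ties no go/no-go decision to the survey target. The two timing rules should nonetheless be reconciled before data are seen, because relaxing the cut-off after late surveys are known would be a post hoc choice.

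**What to change.** Use one anchor (hospital discharge) and one identical window in 6.0, Table 1, Table 2 and 10.3.

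**Smallest change.** Keep the criterion, which is already stated the same way twice, and edit Table 1 and section 6.0 to read: *Post-pilot survey done after hospital discharge and no later than day 7 after discharge.* The cost is less scheduling time for staff. A first follow-up visit can then serve only if it falls by day 7; otherwise the telephone route in 9.2 is needed.

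**Alternative, if the 5-day tolerance is intended.** State the window in the calendar and in 6.0 as one week after hospital discharge (+5 days), that is, days 7 to 12. Define the criterion in 10.3 and Table 2 as completion within that same window, and report the rate by day 7 after discharge as a supporting figure. The cost is a slightly looser criterion, closing up to 5 days later than now. The day-7 figure would also rest on the first permitted day alone, so it could only be supporting.

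Either way the edit is wording only. Recording the date of discharge and of each survey lets the result be checked against the chosen window.

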## **11.0 Withdrawal of Subjects**

Subjects are able to withdraw from the study at any point. They will be given study team contact information to withdraw after agreeing to participate and will be able to terminate their participation in the focus group or interview at any point. Their demographic information will not be used at that point; for focus group participants, it will not be possible to remove their data from the audio transcription; for individual interviewees,

**PROTOCOL TITLE:** *Development and Piloting of Avatar-based Intervention to Support Patients Undergoing Stem Cell Transplantation*

their interview data will be deleted. Subject withdrawal reason(s) will be attempted to be obtained. In certain situations, such as severe encephalopathy or critical illness, patients may be withdrawn from the trial by the investigators due to inability to utilize and interact with the digital avatar device.

## **12.0 Risks to Subjects**

### 12.1 Anticipated Risks

**Aim 1:** Anticipated risks to participants include the potential risk of compromise of participant confidentiality due to use of video conferencing groups. For the focus group associated risks, the study team will explain to participants the procedures that will be employed to ensure privacy and confidentiality, and situations such as the focus group discussions where these are not entirely possible. Procedures that will be taken to ensure confidentiality include de-identifying all the data collected from the focus group and storing in a password encoded database.

**Aim 2:** Anticipated risks to participants include the potential risk of compromise of participant confidentiality and loss of confidentiality of their data collected by the DFCI investigators. Psychological risks include embarrassment and stigmatization if there is inadvertent disclosure of confidential information, and distress due to losing a friendship with the avatar at the end of the hospital stay. While it is very common to develop a friendship with the avatar and ending such a relationship is generally a negative experience, due to the context of the relatively short-term hospital stay, it is expected that patients will overall be happy to be discharged and they will not be led to believe that the avatar will be with them for the long-term.

### 12.2 Unanticipated Risks

Any unanticipated event will be reported to the OHRs. All human subjects will be informed of their right to stop participation at any time. Subjects will be notified of their right not to answer any questions or choosing to no longer participate. If a participant experiences distress, they can contact [name] at [[name]\\[contact]](mailto:[contact]) or [contact] or [name] at [[name]\\[contact]](mailto:[contact]).

## **12.0 Potential Benefits to Subjects**

**Aim 1:** There is no direct benefit expected for participants except for the \$50 gift card.

**PROTOCOL TITLE:** *Development and Piloting of Avatar-based Intervention to Support Patients Undergoing Stem Cell Transplantation*

**Aim 2:** Participants may potentially benefit from participating in the study by being exposed to educational modules pertaining to their care as well as receiving psychosocial support via the avatar. Participants in the third cohort will receive a \$20 Dana-Farber gift card for completion of at least 4 out of 7 educational modules presented by the device to assess the impact of this potential benefit when planning the subsequent randomized trial.

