## 8.0 Procedures Involved

### 8.1 Design/Study Type

**PROTOCOL TITLE:** *Development and Piloting of Avatar-based Intervention to Support Patients Undergoing Stem Cell Transplantation*

[figure not shown]
Aim 1: Focus group.

Aim 2: Single-arm feasibility pilot, with 3 cohorts of 6 patients (18 total).

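### The gift card is offered only to cohort 3, so its effect cannot be separated from avatar version and calendar time without untestable assumptions

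*Combined protocol and SAP*

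**What the plan says.** Section 12.0 (Potential Benefits to Subjects, Aim 2) restricts a $20 card to the third cohort. It is paid for "completion of at least 4 out of 7 educational modules presented by the device to assess the impact of this potential benefit", and the same sentence ties that purpose to planning the subsequent randomized trial.

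Three other sections fix the setting in which the card is given:

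- Section 8.1 describes Aim 2 as a "Single-arm feasibility pilot, with 3 cohorts of 6 patients (18 total").
- Section 6.0 calls it "a phased, iterative user acceptance study with 3 consecutive cohorts of 6 RIC HCT patients each", and says that after each cohort "protocol completion and patient-avatar engagement data will be analyzed".
- Section 10.4 says that "this iterative design will allow for rapid protocol improvements to be deployed to new patients in subsequent cohorts", and gives the aim as "to move towards achieving the success criteria above".

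One of those criteria, in Section 10.3, is the secondary one on modules: "rate of completion of 80% of the HCT educational modules of 75" percent. Section 10.3 ties satisfaction to the final cohort but names no cohort for module completion. Section 10.1 plans comparisons between groups without defining the groups, and specifies no analysis of the card.

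**The concern.** The card has a stated purpose, which is to learn its impact for a later trial. That needs patients with and without the card who are otherwise comparable. Here every patient offered the card comes last in time and has the most revised avatar, and the revision is itself meant to raise the outcome that the card might raise. No cohort-3 patient goes without the offer, and no earlier patient receives it.

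If completion rises in cohort 3, the trial team may credit the card and carry an untested incentive into the randomized trial. If it does not rise, the card may be dropped although a less successful revision could have masked its effect.

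**Working it through.** **The plan's own figure.** The Aim 2 sample size rests on accrual (Section 10.2): 162 × 0.33 = 53.5, stated as 54; 54 × 0.33 = 17.8, stated as 18; and 3 × 6 = 18. It reproduces. The documents give no effect size, power or test for the card.

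**Separability with cohorts of six.** Take revision at cohort boundaries and write the model as intercept + cohort 2 + cohort 3 + card. The cohort-3 term carries avatar version and period. Card = 1 exactly when cohort 3 = 1, so two of the four columns are identical and the rank is 3. The rank is still 3 with 60 or 6000 patients per cohort.

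**What more patients would do.** Assume that the true card effect is zero and that revision alone raises completion from 50% to 75%. Cohort 3 then differs from cohorts 1-2 by 25 points for reasons unrelated to the card. The chance of p ≤ 0.05 is about 10% at 6 against 12 (Fisher's exact test) and about 100% at 600 against 1200 (normal approximation). A larger sample only makes the wrong attribution more certain.

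**Two routes that formally separate the card.** Variances are in units of the residual variance.

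1. *Linear trend over cohorts.* The estimate is the cohort-3 mean minus (2 × cohort-2 mean − cohort-1 mean). Its variance is (1 + 4 + 1)/6 = 1.0, against 1/6 + 1/12 = 0.25 for the simple contrast of cohort 3 with cohorts 1-2. It extrapolates from two cohorts, cannot be tested and is not in the plan.
2. *Revision after every five patients.* Section 10.4 speaks of groups of five, while Sections 1.2, 4.0, 6.0, 8.1 and 19.0 give cohorts of six. Taken literally, changes follow patients 5, 10 and 15. Patients 11-12 (no card) and 13-15 (card) then share a version, and the model with three version terms and card has full rank (5 of 5). The contrast is 2 patients against 3, with variance 1/2 + 1/3 = 0.83.

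**Precision if confounding is assumed away.** Suppose that revision and time have no effect, and that 6/6 complete with the card and 8/12 without. The difference is 100% − 66.7% = 33.3 points, with a Newcombe 95% interval of −10.3 to +60.9. This is one illustrative outcome, not a forecast.

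**Payment trigger against endpoint.** The trigger is 4/7 = 57%. If seven modules are delivered, the endpoint needs 0.8 × 7 = 5.6, so 6 of 7 (86%). The card does not reward the endpoint as defined, and whether it would move the endpoint is unknown.

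**The case against.** The strongest reply is that this is a small feasibility pilot. The card is not an objective, endpoint or success criterion, and no hypothesis about it is tested. The sentence sits in a section on benefits, so its purpose may be only an informal look. Section 6.0 already foresees analysis after each cohort. All of that is fair and limits the weight of the point. It does not remove it, because a by-cohort look can show a difference but cannot say what caused it, and the protocol states impact as the purpose.

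A reader might infer more than the documents support:

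- *That the card effect is unidentifiable under any assumption.* This is too absolute. A linear trend, or literal revision after every five patients, gives full rank, though through an untestable assumption or a contrast of 2 against 3 patients. If nothing were changed after cohort 2, the version component would vanish, but calendar time would still coincide with the card.
- *That the card undermines the trial's main result.* The primary endpoint is retention. The card is tied to module completion, at a level below the secondary criterion.
- *That the card could tip the overall module-completion rate past 75%.* Any rise in cohort 3 could do that, whatever its cause, so this is not evidence about the card.
- *That the later trial will adopt the card because of this comparison.* Nothing in the protocol says so.

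**Conclusion.** The point holds in a limited form. As designed, a card effect cannot be told apart from avatar version and calendar time without untestable assumptions, and enlarging the same design would not help. This rests on cohorts of six with revision at cohort boundaries, which is how most of the protocol reads. If revision really followed each five patients, the usable comparison would be too small to inform anything. What is affected is the planning of the later trial and the reading of one secondary criterion; the primary retention endpoint is untouched. The correction is worth making because a stated purpose cannot be met and the remedy is cheap.

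**What to change.** 1. In Section 12.0 (Potential Benefits to Subjects), replace the purpose of assessing impact with a descriptive one, such as: to describe module completion when a gift card is offered. Add: because the card, the avatar version and calendar time change together, a difference in cohort 3 will not be attributed to the card.
2. In the final report, give the proportion of patients completing at least 80% of modules, and the proportion reaching 4 of 7, separately for cohorts 1-2 (no card) and cohort 3 (card). Show exact 95% intervals, beside the pooled rate.
3. Reconcile the groups of five in Section 10.4 with the cohorts of six elsewhere.

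The cost is a few sentences and one block of a table, with no extra patients. A causal statement about the incentive is given up, and the cohort rates stay imprecise (exact 95% interval 35% to 90% at 8/12, and 54% to 100% at 6/6).

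Randomizing the card within cohorts would identify its effect, but not usefully at this size. The variance would be 1/9 + 1/9 = 0.22 for 9 against 9 across all cohorts, or 1/3 + 1/3 = 0.67 for 3 against 3 within cohort 3. Detecting an assumed 75% against 90% with 80% power at two-sided 0.05 needs about 100 per arm. That question belongs in the later trial.

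The table needs patient-level module counts. Section 9.2 says "We will collect data on feasibility outcomes (retention, satisfaction, completion of modules) via post-pilot survey", but the survey in Appendix A has no item that counts modules. That gap exists with or without the card and should be settled as a separate item.
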